**Figure 1. Study design**

The study will be partially blinded: participants and study staff, including the study statistician, will be blinded as to the assignment for those in the intervention and placebo arms. In contrast, no one will be blinded as to assignment to the open control arm. (Note that it is not feasible to maintain blinding for the open control arm even among the data analysts given the planned grouping of the arms for the data analyses.) DMPA has a duration of protection of 12 weeks. Women in the intervention or placebo arm will be counseled to refrain from initiating hormonal contraception in the next 6 weeks and to refrain from initiating DMPA in the next 12 weeks. Study staff will use the "Contraceptive choice information sheet" to explain the contraceptive methods that participants can use depending on whether they are assigned to an arm that receives a shot or the arm that does not receive a shot. All participants will be counseled to use condoms post-delivery to avoid a repeat pregnancy (as they either received no shot or could have received a placebo shot). Participants will receive a supply of condoms for either 12 weeks (intervention or placebo arm) or 6 weeks (open control arm), and will be referred to receive DMPA at either 12 weeks (intervention or placebo arm) or 6 weeks post-delivery (open control arm).

Data collection, which will occur at enrollment and through 12 months of follow up, will involve 1) questionnaires on demographics, characteristics and behaviors, lactogenesis, breastfeeding and contraception use and 2) infant anthropometric measures (Table 1).

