**Table 1. Data collection by objective, location, schedule and mode of collection, and compensation.**

Objective	Data collection	Location	Schedule and mode of collection	Compensation
1,2	Enrollment Questionnaire	Participating hospital	Self-administered within 48 hrs of delivery	\$80 in cash at OSUWMC; \$80 in electronic gift card at Emory-affiliated Hospital
1	Milk Let-Down Questionnaire	Participating Hospital / text, telephone, email	Interviewer administered ≤3 times daily in person at OSUWMC or Emory-affiliated hospital, then daily via text, telephone or email during the first 7 days postpartum until lactogenesis stage II occurs	One payment of \$30 in electronic gift card at all sites
1,2	Follow-up Questionnaire	Online	Self-administered at 1, 2, 4, 6, 9 and 12 months. Questionnaires at 1, 6 and 12 months include infant anthropometric measures* from well-child visit data	\$10 per interview in electronic gift card at all sites
1	Infant adiposity (PEA POD) and other infant measures*†	OSUWMC only	Measured by trained study staff at 4 months of age	\$40 in gift card, a branded gift (e.g., a cell phone popsocket or a pen with light) worth less than \$4.00, and either parking pass or transportation by cab to appointment

OSUWMC = Ohio State University Wexner Medical Center; \*Includes weight, length, head circumference; †Visit not completed by participants who delivered at an Emory-affiliated Hospital

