**Table 2. Location for recruitment, screening and enrollment by prenatal and postpartum status and type of location**

Women	Type of location	Location
Prenatal	Prenatal care at primary obstetrical facilities that refer to a participating hospital for delivery	
 
• Hospital obstetrics-gynecology outpatient clinic
 
• Faculty practices
 
• Primary One health centers
 

	Local classes for pregnant women in the community	
 
• Lactation, birthing and prenatal yoga classes
 

Finally, secondary outcomes will include infant measures collected during the follow-up questionnaire (using maternal reports of data from well-child visits) and during the 4-month visit at OSUWMC. Participants enrolled at an Emory-affiliated hospital will not complete a 4-month visit because the site lacks the ADP system. The latter will include the following: 1) percent fat mass (%FM) and fat-free mass (FFM%) measured using the validated, non-invasive whole-body air displacement plethysmography (ADP) system; 2) length with a SECA 416 digital infantometer; 3) head circumference with metric tape; 4) body weight with SECA 727 digital scale; and 5) skinfold with Holtain calipers. We will ensure consistently high-quality measurement by regular monitoring, assessing reliabilities, and refresher training.	Postpartum	Through MyChart Hospital	
 
• Tour of study hospitals during pregnancy
 
• OSUWMC and participating Emory-affiliated hospitals
 

---	------------	--------------------------	---

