Participants will be referred for DMPA at 12 weeks if in the intervention or placebo arms and at 6 weeks if in the open control arm. Participants will receive referrals for financial assistance for DMPA as appropriate. Participants will be counseled to use condoms for all sexual intercourse before receiving DMPA and will receive a supply of condoms for 12 weeks (intervention or placebo arms) or 6 weeks (open control arm). Interviewers will administer the short “Milk Let-Down Questionnaire” up to three times daily in person before discharge or until lactogenesis II occurs.

**Follow up.** If lactogenesis II does not occur before hospital discharge, participants will be asked to complete the “Milk Let-Down Questionnaire” daily via telephone, text or email for the first 7 days postpartum until the event occurs.

Participants will be instructed to complete an online “Follow-up Questionnaire” at 1, 2, 4, 6, 9 and 12 months post-delivery. The “Follow-up Questionnaire” will collect data on breastfeeding behaviors and perceptions; contraception use; and infant physical measurements from well-child visits. If the participant does not have the information from her infant’s well-child visit on-hand or if the information that she provides is incomplete or appears to be inaccurate, we will extract the data on the infant’s weight, length and head circumference from the medical records at their pediatrician’s office.

Participants enrolled at OSUWMC will be asked to return with their infant to OSUWMC for a four-month visit, during which infant measures will be collected (infant adiposity via PEA POD, weight, length, head circumference and skinfold) and recorded on the “Four-month Visit Form.” If women have not already completed their 4-month online “Follow-up Questionnaire” at the time

of the in-person visit, they will be instructed to do so using a computer established for this purpose at OSUWMC.

**Compensation.** Participants will receive compensation (amounts specified in Table 1) for their time and travel expenses. The compensation amounts are in-line with recent research with similar populations.

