## **E. Incidents and Incident Reporting**

**Study staff will record information on any adverse events (AEs) that are classified 1) as possibly, probably, or definitely related to study participation and as unexpected or 2) as serious.** Adverse events (AEs) are defined as any untoward health-related reaction, effect,

toxicity, or abnormal laboratory result that a study participant experiences during the course of a study that is new or a worsening of a baseline condition.

An *unexpected* AE is one whose specificity or severity is not listed in the DMPA package insert (i.e., bleeding irregularities, bone mineral density changes, cancer risks, thromboembolic disorders, ocular disorders, ectopic pregnancy, and anaphylaxis). Information on expected AEs will be recorded on study data collection forms, but these events will not be reported to the relevant IRBs and NIH unless the event is also serious or is an unanticipated problem involving risks to subjects or others (UPIRTSO).

An AE is considered *serious* if it is fatal or life-threatening, requires in-patient hospitalization or prolongation of an existing hospitalization, results in a persistent or significant disability or incapacity, is a congenital anomaly or birth defect, jeopardizes the participant or requires intervention to prevent one of the outcomes listed above, or any other event deemed serious by the investigator. Study personnel will report any AE to the PI, who will determine 1) its relatedness to study participation and 2) its seriousness.

All serious adverse events (SAEs) will be reported in an expedited manner to the PI. If it is determined that the SAE is unanticipated and anything other than “not related” (i.e., possibly, probably or definitely related), then the PI, or designee, will notify the IRBs of record and the NIH of the event. Non-serious AEs will be recorded on data collection forms but do not require expedited reporting unless they are classified as UPIRTSO.

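### Adverse events are to go on data collection forms, but no scheduled form or contact is described as asking about maternal or infant health events, so capture after the first week is passive as described

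*Combined protocol and SAP*

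**What the plan says.** Section VI.E (Incidents and Incident Reporting) deals with what happens once an event is known. Of expected events it says: "Information on expected AEs will be recorded on study data collection forms". Of non-serious events it says: "Non-serious AEs will be recorded on data collection forms but do not require expedited reporting unless they are classified as UPIRTSO". The route to the investigator is "Study personnel will report any AE to the PI". The section names no form and gives no question, time point or recall period by which staff would learn of an event.

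Section V describes the data collection itself. The Overview (V.A) sums it up, from enrollment to 12 months, as "questionnaires on demographics, characteristics and behaviors, lactogenesis, breastfeeding and contraception use and 2) infant anthropometric measures (Table 1"). Table 1 gives the Follow-up Questionnaire as online and "Self-administered at 1, 2, 4, 6, 9 and 12 months". Section V.D says that this questionnaire "will collect data on breastfeeding behaviors and perceptions; contraception use; and infant physical measurements from well-child visits". The four-month visit is described as infant measurement and takes place at one centre only: "Participants enrolled at an Emory-affiliated hospital will not complete a 4-month visit because the site lacks the ADP system".

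Section VI.F has the Data Safety Monitoring Committee review accumulated data after an initial subset and after half of the participants are enrolled. It has no stopping guidelines and relies on its own judgment. The statistical section (V.E) contains no adverse-event analysis.

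**The concern.** The two parts of the protocol do not meet. VI.E relies on data collection forms to hold adverse events, while the descriptions of those forms in V.A and V.D mention no health-event item for mother or infant. If the trial runs as described, a hospital admission at three months becomes known only if the mother raises it unprompted or staff come across it by chance.

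This matters for three reasons:
- The expedited process for serious events can act only on events that reach staff.
- A committee that decides on judgment, without numerical guidelines, depends on the completeness of what it is shown.
- The protocol's conclusion expects the results to help harmonise international guidance, so readers will look for a safety statement. A low or similar count of unsolicited events gives weak support for one.

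This is separate from which known events must be recorded. On that, the opening rule of VI.E is narrower (events classified "as possibly, probably, or definitely related to study participation and as unexpected or 2) as serious") than its later sentences on expected and non-serious events. Settling that rule would not cause any event to be asked about.

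**Working it through.** **Step 1. Described content of each form and contact.**

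| Instrument or contact | Where described | Described content | Health events asked? |
|---|---|---|---|
| Enrollment Questionnaire | Table 1, V.D | Background, reproductive history, attitudes, breastfeeding intentions | Not described |
| Milk Let-Down Questionnaire | Table 1, V.C, V.D | Lactogenesis; stops at the event or day 7 | Not described |
| Follow-up Questionnaire, six time points | Table 1, V.D | Feeding, contraception, infant size | Not described |
| Four-month Visit Form, OSUWMC only | Table 1, V.C, V.D | Adiposity, weight, length, head circumference, skinfold | Not described |
| Paediatric record extraction | V.D | Conditional; weight, length, head circumference | Not described |
| Reminders, contact tracing, telephone option | V.D, VIII | Retention and questionnaire completion | Not described |
| Log and report form for unanticipated problems | VI.E | Records incidents already known | Does not elicit |

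No row describes a question about admissions, emergency visits or other health problems.

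**Step 2. Blinding and contact schedule.** Intervention and placebo women are blinded, as are study staff, and both arms have the same contacts (V.A, V.D). Open-control women and staff know the assignment. Randomisation is of individuals, so the OSUWMC-only visit falls on all arms alike in expectation.

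**Step 3. Illustration of lost sensitivity, DMPA versus placebo.** The protocol gives no adverse-event rates or capture fractions; those below are assumptions. The sample size section gives n = 143 per arm. The test is two-sided at 5%.

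Power = Φ[(d − 1.96·SE0)/SE1], where SE0 = √[p̄(1−p̄)(1/n₁+1/n₂)], SE1 = √[p₁(1−p₁)/n₁ + p₂(1−p₂)/n₂], and each true rate is first multiplied by the capture fraction c.

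Worked case: true rates 20% and 10%, c = 0.5, so the observed rates are 10% and 5%. Then d = 0.05, p̄ = 0.075, SE0 = √(0.075 × 0.925 × 2/143) = 0.0311 and SE1 = √[(0.09 + 0.0475)/143] = 0.0310. Power = Φ[(0.05 − 0.0611)/0.0310] = Φ(−0.36) = 36%.

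| True rates | c = 1 | 0.75 | 0.50 | 0.25 |
|---|---|---|---|---|
| 20% v 10% | 66% | 52% | 36% | 20% |
| 10% v 5% | 36% | 28% | 20% | 12% |

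Equal under-capture leaves the expected risk ratio at 2; only precision is lost.

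**Step 4. Illustration of differential reporting, no true effect.** Assume capture of 60% in both injection arms and 40% in open control. The expected observed ratios are:
- DMPA v placebo: 0.6/0.6 = 1.0
- Injection arms v open control: 0.6/0.4 = 1.5
- DMPA v placebo and open control pooled equally: 0.6/[(0.6 + 0.4)/2] = 1.2

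For injection arms v open control (286 v 143), the chance of a significant false excess is about 12% at a true rate of 10% and 23% at 20%. If the capture fractions are swapped, the injection v open-control ratio becomes 0.4/0.6 = 0.67. Nothing in the protocol indicates which direction applies.

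**The case against.** The strongest reply is that the questionnaires are not in the document. V.A and V.D give topic summaries, and VI.E refers to data collection forms in a way that suggests adverse-event fields may exist somewhere. A manual of operation and a monitoring charter are also mentioned but not shown. This stands: a reader might infer that no form asks about health events, but the documents support only that none is described as asking.

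Staff also have other contacts after discharge: daily messages in the first week until lactogenesis, reminders, contact tracing, a telephone option, and the visit at OSUWMC. So it would be too strong to say that only volunteered events can become known. Some will be learned incidentally, although none of these contacts is set up to ask.

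A reader might further infer that the arms cannot be compared for safety. That does not follow. DMPA and placebo share blinding and schedule, and Step 4 gives a ratio of 1.0 for that contrast when the two arms report alike. Nor does the OSUWMC-only visit bias the arms, because women at each centre are individually randomised.

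The outcomes that motivate the trial are solicited in every arm: lactogenesis, feeding, supplementation and infant growth. The protocol also classes the study as minimal risk, and the trial was not sized for adverse events. With full capture, power is still only 36% for 10% versus 5%. All of this limits the consequences. It does not supply the missing description of how other health events are found.

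**Conclusion.** The concern holds as a gap in described ascertainment. On the plan's own account of its forms and contacts, maternal and infant health events outside feeding and growth are not actively sought after the first week. The serious-event process and the monitoring committee would therefore work from incomplete data.

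The cost differs by comparison. DMPA versus placebo loses sensitivity but is not clearly biased. Comparisons involving the open-control arm, including pooling it with placebo, are also exposed to differential reporting of unknown direction. The lactation, feeding and growth outcomes are unaffected.

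No figure in the protocol measures the loss. The power and ratio figures above are illustrations under assumed event rates and capture fractions, and the conclusion does not rest on them. If a form already carries such items, naming the form, its questions and its time points would settle the point. If none does, the change below should be made.

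**What to change.** Add the same short yes/no items, each with a date, to all six Follow-up Questionnaires, in all three arms and at both OSUWMC and the Emory-affiliated hospitals. The recall period is since the last questionnaire (since delivery for the first).
- **Mother:** any hospital admission, emergency visit or new medical problem.
- **Infant:** any hospital admission, emergency visit or clinician-diagnosed problem.

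State in V.D that these items are asked, and in VI.E that every yes enters the event process described there. Add to V.E a table of solicited events by randomised arm, for the monitoring committee and the final report. Make DMPA versus placebo the main safety contrast, and interpret contrasts with open control in light of its unblinded status. Unsolicited events should be shown separately.

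The cost is a few REDCap fields on questionnaires already scheduled, a sentence in each of V.D and VI.E, and one table. The downside is slightly longer questionnaires, against the stated aim of brevity, and some staff time to follow up yes answers. Treatment, endpoints and sample size do not change.

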## **F. Data Safety and Monitoring Plan**

**The Regulatory and Ethics Core of The Center for Clinical and Translational Science (CCTS) at OSU will assemble a Data Safety Monitoring Committee (DSMC) – consisting at minimum of a research ethicist / research subject advocate, biostatistician, and obstetrician-gynecologist – to independently monitor the safety of the study. The DSMC will be chaired by [name], who is Professor in the Department of Internal Medicine at OSU and the Director of the Regulatory Program at CCTS. The DSMC will convene before study initiation and, during this initial meeting, the DSMC will provide recommendations regarding the protocol application and will develop and approve the DSMC Charter for the trial. After trial initiation, the DSMC will review the accumulated data after an initial subset of participants have been enrolled and after half of the participants have been enrolled. The DSMC**

will evaluate participant safety and study conduct and progress and will make recommendations to the sponsor and investigators concerning the trial continuation, modification or termination. No specific stopping guidelines will be presented with the data, and stopping early for safety reasons will be based on the judgment of the DSMC.

## **VII. Protocol Registration**

We will prospectively register the trial at the Protocol Registration System ([www.clinicaltrials.gov](https://www.clinicaltrials.gov)) before enrolling any subjects.

## **VIII. Internal Validity**

A primary limitation of the trial involves potential issues of generalizability. For example, we are restricting the study to exclude infants who are preterm, low birthweight, or have apparent health complications. Consequently, our findings cannot be extended to infant subgroups arguably most in need of the intervention. Although breastfeeding could be especially important for these subgroups, their inclusion could hinder our ability to detect differences attributable to DMPA exposure. A future study would focus on these special groups. Another potential issue is the linkage, albeit controversial, between DMPA and increased risk of HIV acquisition found in non-randomized trials. However, even if the ongoing RCT eventually supports a causal relationship, DMPA is a popular method that can be expected to continue to have an important role in the contraception method mix.

The trial will not answer other research questions that may be of interest. For example, we will not evaluate whether early administration of DMPA affects milk composition. Prior assessments have been unable to interpret the clinical significance of any difference detected in milk composition. For this reason, we are focusing on outcomes with clearer clinical significance. While other breastfeeding outcomes are important to maternal and infant health, we selected the primary outcome, timing of lactogenesis stage II, because it is closely tied to the possible mechanism by which DMPA exposure could impair lactation. Furthermore, this outcome is less susceptible to bias than other possible breastfeeding outcomes. For example, breastfeeding duration could be biased if even a minor proportion of participant attrition occurs during follow up and if this attrition were differential by study arm.

We could experience logistical challenges while fielding the trial. We plan to randomize women within 48 hours of delivery. However, to reflect real-life, clinical circumstances, we will randomize women within 96 hours of delivery, if needed. In this case, we would conduct sensitivity analyses to determine whether the timing of the initial DMPA injection affects the primary outcomes.

We will implement strategies to maximize study retention that has been effective in our previous clinical trials. These include collecting (and routinely confirming) detailed contact information to generate follow-up reminders about study activities and visits; conducting contact tracing of participants who fail to complete on-line questionnaires or the in-person 4-month visit; providing the option of completing the questionnaire via telephone for any participant who prefers this mode for any reason (e.g., lack of internet access); streamlining procedures to allow participants to complete follow-up assessments quickly; designing data collection instruments to be as concise as possible so as to not overburden the participants and thereby increase the risk of response error; and providing payments to compensate for time and travel costs incurred by the participants.

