## **III. Objectives**

**Objective 1: To determine the effect of immediate postpartum initiation of DMPA on breastfeeding.** We hypothesize that administration of DMPA immediately postpartum (i.e., before hospital discharge) will not impair breastfeeding compared to administration beginning at 12 weeks post-delivery. To increase the likelihood of detecting a negative effect if one exists, we will evaluate the primary outcome, timing of lactogenesis stage II (onset of copious milk secretion, usually occurring within 96 hours postpartum), as well as a range of secondary outcomes: breastfeeding duration, perceived need for supplementation, use of supplementation, perceived adequacy of milk production, and infant anthropometric measures, including body composition with whole-body air displacement plethysmography (OSUWMC site only). Sensitivity analysis will evaluate 1) excluding women in the open control arm and 2) determining whether the findings differ by race.

**Objective 2: To determine the effect of immediate postpartum initiation of DMPA on contraception use.** We hypothesize that putative DMPA use (i.e., blinded assignment to intervention or placebo arms) will put women on a better trajectory of contraception use by intervening during a time when they likely are highly motivated to avoid pregnancy. In contrast, women who are assigned to start DMPA after a delay risk losing motivation to initiate use. To test this hypothesis, we will compare prevalence of use of a highly-effective contraceptive method at 12 months post-delivery between women in the intervention and placebo arms versus the open control arm. Secondary outcomes will include DMPA use at 12 months. Sensitivity analyses will evaluate 1) whether the findings differ by race and 2) whether the findings differ after restricting the intervention and placebo arms to the subset of women who believe that they were in the intervention arm.

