#### IV. Literature

##### A. Literature in Support of Objective 1: The relationship between immediate postpartum initiation of DMPA and lactation.

Because delayed lactogenesis stage II is associated with a range of poor breastfeeding outcomes (failure to initiate, reduced duration, and use of supplements), identifying any negative effect of progestin on lactogenesis would be important. In theory, progestin could inhibit the process. Production of progesterone by the adrenal glands, ovaries and placenta increases during pregnancy. Plasma progesterone levels do not decrease until after delivery of the placenta, after which time, levels decline rapidly, reaching follicular phase levels after 2-3 days. This decline, along with decreased estrogen levels and infant suckling, is thought to trigger lactogenesis. Cases of placental retention, in which lactogenesis has been delayed up to three weeks, support this physiologic mechanism. Also, exogenous progesterone given around the expected parturition time in rats or after fetus removal in ewes inhibits milk secretion; in contrast, no inhibitory effect occurred in rat models when progesterone was given after the establishment of lactation. Note, though, that progesterone and the synthetic progestogen, medroxyprogesterone acetate, used in the contraceptive injectable are different compounds, which are known to produce different effects in women; thus, **findings from trials on progesterone use in animals are suggestive but cannot be assumed to represent the effects of DMPA use in women.**

**A recent systematic review found no RCTs in humans on the effect of immediate postpartum initiation of DMPA on lactation.** Three RCTs compared immediate postpartum use of a progestin-only method other than DMPA with the initiation of the same or a different hormonal method later during the puerperium. The three trials made the following comparisons: etonogestrel implant used immediately postpartum versus DMPA at 6 weeks postpartum;

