**Non-randomized evidence regarding the effect of immediate postpartum DMPA exposure on lactation outcomes is inconclusive.** Ten observational studies compared breastfeeding outcomes between women choosing to use DMPA starting within the first 6 weeks postpartum compared to women using another or no method. In six of these studies, the upper window for starting DMPA ranged from five days to four months postpartum. None of these studies found impaired lactation outcomes (and three found DMPA to be associated with increased breastfeeding duration). However, because women in the six studies received DMPA after the typical window for lactogenesis stage II, their findings do not shed light on the potential effects of DMPA initiated before hospital discharge. The remaining four observational studies evaluated the effects of earlier DMPA administration, specifically 1-2 days postpartum, within 72 hours postpartum, or at the time of or before hospital discharge. These study findings were mixed in that early DMPA administration was associated with longer mean breastfeeding duration; with less breastfeeding continuation at four weeks or at three months; or with no difference in duration. Furthermore, these non-randomized studies do not support firm conclusions because 1) they did not control for potential confounders related to women choosing to start DMPA use, which could have introduced substantial bias, and 2) they did not employ standardized, validated outcomes.

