## B. Study Population

We will enroll a convenience sample of 800 women. Women can enroll either prenatally or postpartum before their hospital discharge.

To enroll prenatally, women need to meet the following eligibility criteria:

- 1) Intend to deliver in the Labor and Delivery Unit at a participating ;
- 2) Are ≥18 years of age;
- 3) Speak English;
- 4) Intend to breastfeed, or express milk for their infant, for ≥6 months;
- 5) Do not want to become pregnant within the first 12 months after delivery;
- 6) Want to start use of DMPA immediately after delivery before discharge; **AND**

- 7) Intend to reside in Ohio for those who deliver at OSUWMC or intend to reside in Georgia for who deliver at an Emory-affiliated Hospital for the first 12 months after delivery.

Women will be excluded if they have any contraindications to DMPA (per package insert), which consist of the following:

- 8) Undiagnosed vaginal bleeding;
- 9) Known or suspected malignancy of breast;
- 10) Active thrombophlebitis, or current or past history of thromboembolic disorders, or cerebral vascular disease;
- 11) Liver dysfunction or disease; **OR**
- 12) Known hypersensitivity to Depo-Provera.

Women who enroll prenatally will need to rescreen following delivery to confirm their eligibility. Women enrolling after delivery or who are rescreening will need to meet criteria 2-12 above as well as the following eligibility criteria:

- 1) Are a postpartum patient in the Labor and Delivery Unit at OSUWMC or participating Emory-affiliated Hospital; **AND**
- 2) Have delivered a term, singleton infant of  $\geq 2500$  grams without any apparent health concerns.

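### Women whose milk came in before randomisation dilute the 6-hour noninferiority contrast, and no analysis of women still at risk is prespecified

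*Combined protocol and SAP*

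**What the plan says.** Under Objective 1 (section III) the hypothesis is that giving DMPA "immediately postpartum (i.e., before hospital discharge) will not impair breastfeeding compared to administration beginning at 12 weeks post-delivery". The same paragraph states: "To increase the likelihood of detecting a negative effect if one exists, we will evaluate the primary outcome"; the sentence then goes on to list secondary outcomes. Section VIII says that time to lactogenesis II was chosen as primary "because it is closely tied to the possible mechanism by which DMPA exposure could impair lactation".

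Section V.B sets the post-delivery criteria: "Are a postpartum patient in the Labor and Delivery Unit at OSUWMC or participating Emory-affiliated Hospital", and a healthy term singleton of at least 2500 g, alongside the general criteria and contraindications. None concerns milk onset. Section V.C asks, straight after enrolment, whether milk has come in and, if so, records the hour since delivery as the outcome. Section V.E expects the outcome for every randomised woman. It accepts noninferiority if the upper 95% confidence limit for the mean difference, intervention minus the two other arms combined, is below 6 h. Its sensitivity analyses drop the open control arm, adjust for covariates, examine Black race and impute missing data. None restricts to women still at risk.

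On timing, section VIII plans randomisation within 48 h, then says that "to reflect real-life, clinical circumstances, we will randomize women within 96 hours of delivery, if needed". It continues: "In this case, we would conduct sensitivity analyses to determine whether the timing of the initial DMPA injection affects the primary outcomes".

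**The concern.** A woman whose milk is already in when she is randomised contributes no treatment effect, whichever arm she joins. In a superiority trial, including her would be conservative. In a noninferiority trial, it moves the contrast towards success.

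The protocol itself treats the timing of exposure relative to onset as important. Section IV.A reports that "no inhibitory effect occurred in rat models when progesterone was given after the establishment of lactation" (animal data that it calls only suggestive). It sets aside six observational studies because their participants were given "DMPA after the typical window for lactogenesis stage II, their findings do not shed light on the potential effects of DMPA initiated before hospital discharge". A noninferiority result here is likely to be read as showing that DMPA does not delay lactogenesis II. That statement concerns women in whom a delay was still possible, and the plan has no analysis that speaks to them directly.

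The one nearby safeguard, the timing analysis in section VIII, is triggered only if the window is extended. It has no stated method or margin and does not mention prior onset. It would not run if injections clustered just before 48 h.

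**Working it through.** **Inputs.** From section V.E: mean 65 h, SD 18 h, margin 6 h, two-sided 95% CI, 143 women per arm, so 143 against 286. Assumed here: normally distributed onset times, and every injection-time pattern below.

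**The plan's own figures.** SE = 18 × √(1/143 + 1/286) = 1.844 h. Power at zero difference = Φ(6/1.844 − 1.96) = 90.2% (stated 90%). With 128 against 256 it is 86.8% (stated 87%); with 143 against 143 it is 80.5% (stated 80%). All reproduce.

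**Share with prior onset.** At h hours after delivery it is Φ((h − 65)/18): 5.4% at 36 h, 17.2% at 48 h, 65.1% at 72 h and 95.7% at 96 h. For injections spread over a window, f is the average of this over the window. It averages 0.618 over 48–96 h.

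**Dilution.** With mean delay d in at-risk women, the all-randomised difference is d × (1 − f). Setting d = 6 h, the chance of declaring noninferiority is Φ(6f/1.844 − 1.96), which is 2.5% when f = 0.

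| Assumed injection times | f | 6 h appears as | Chance of noninferiority |
|---|---|---|---|
| Even over 6–48 h | 0.040 | 5.8 h | 3.4% |
| Even over 24–48 h | 0.066 | 5.6 h | 4.1% |
| Even over 36–48 h | 0.105 | 5.4 h | 5.3% |
| All at 48 h | 0.172 | 5.0 h | 8.1% |
| 10% over 48–96 h, rest 6–48 h | 0.097 | 5.4 h | 5.0% |
| 20% over 48–96 h, rest 6–48 h | 0.155 | 5.1 h | 7.3% |
| 30% over 48–96 h, rest 6–48 h | 0.213 | 4.7 h | 10.3% |

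Worked example, all at 48 h: 6 × (1 − 0.172) = 4.97 h; Φ(6 × 0.172/1.844 − 1.96) = Φ(−1.40) = 8.1%. Of 429 women, about 0.172 × 429 = 74 would have prior onset; for 6–48 h, about 0.040 × 429 = 17.

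**Checks.** Simulation (20,000 trials per scenario, pooled t-based interval) gives 3.5%, 5.0%, 7.7% and 10.3% at 0, 10%, 20% and 30% late. An analysis restricted to at-risk women stays at 2.3–2.6%. A constant delay is not needed: if it builds up over 12 or 24 h after injection with the same 6 h mean, the figures are 3.5–3.7%, 5.1–5.3%, 7.5% and 10.2–10.5%. Lognormal or gamma onset times give 3.0–3.1% for 6–48 h, 7.7–8.1% at 48 h and 6.9–7.1% at 20% late.

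**Order of recording and allocation.** Section V.C asks about onset straight after enrolment, and section V.D reveals the arm upon enrolment. Sections V.A and V.B also use enrolment for a step before randomisation, which may be prenatal. So the text does not settle whether onset status is recorded before the arm is known.

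**The case against.** The strongest reply is that nothing is wrong with the planned test. Objective 1 states one hypothesis, about DMPA before discharge, and the all-randomised comparison answers it with the stated error. This stands. A reader might infer from the table that the primary test has an inflated type I error. The documents do not support that: every figure above 2.5% is measured against an effect in at-risk women that the plan never adopts as its target. The wording in sections III and VIII about detecting harm and mechanism explains the choice of outcomes; it defines no population. The full sentence on the six earlier studies also contrasts late exposure with DMPA before discharge, which is the trial's own policy.

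Second, the effect is small if injections are spread within 48 h, and section VIII does plan a timing analysis if the window is extended. Both are fair. The larger figures need clustering near 48 h or a sizeable late share, and nothing in the documents says that either will occur. Equally, nothing excludes them.

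Third, the 6 h margin was set for all randomised women. With all injections at 48 h, an all-randomised limit of 6 h corresponds to about 6/(1 − 0.172) ≈ 7.25 h in at-risk women, and no section says which limit applies to that subset. It is therefore tempting, but not supported, to demand that an at-risk test against 6 h must also pass. Such a co-requirement would lower power for the combined statement from 90% to about 83–88% at 0–30% late (normal).

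**Conclusion.** The concern holds as a limit on interpretation. The primary analysis is valid for the before-discharge policy effect. By itself it cannot show that DMPA does not delay lactogenesis II in women still at risk, because women with prior onset pull the contrast towards noninferiority.

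The size is minor for injections spread within 48 h (a 6 h delay appears as 5.6–5.8 h) and material if injections cluster at 48 h or 20–30% fall at 48–96 h (4.7–5.1 h). These figures rest on the plan's mean and SD, a normal distribution and assumed injection times. They are scenarios, not predictions. That prior onsets enter the primary analysis is itself inferred: no criterion excludes these women, section V.C times their onset, and section V.E expects the outcome for all randomised women. What justifies a change is that the remedy is cheap and uses data that the trial already collects.

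**What to change.** 1. Keep the all-randomised analysis as primary, and state that it targets the before-discharge policy effect.
2. Ask the existing milk-onset question, with the hour, before the allocation is revealed. Onset status is then a pre-treatment variable and the restricted comparison stays randomised. This matters because the open control arm is unblinded.
3. Prespecify, whether or not the window is extended, a supportive sensitivity analysis in women with no onset recorded before allocation. Report the mean difference and 95% CI against the same 6 h reference. Do not make it a co-requirement for success.
4. If that analysis does not exclude a 6 h delay, limit the conclusion to the policy effect.
5. Report the share with prior onset by arm and the delivery-to-injection times.
6. Reconcile the time windows in sections II, V.A (Table 1), V.D, VI.A and VIII. Some give 48 h without qualification, one gives it as the ideal, and one allows 96 h.

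Cost: one question may have to move, and one analysis is added by a short amendment. Eligibility, sample size, Objective 2 and the 90% power of the primary test are unchanged. Simulated power of the supportive analysis at zero effect runs from about 92% with none late to 86% at 30% late (normal), or from 90% to 81–82% with lognormal or gamma onset times.
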